| | 5.5 SAMPLE SIZE AND POWER | 12 |
| 6 | SAFETY MANAGEMENT | 14 |
| | 6.1 CLINICAL ADVERSE EVENTS | 14 |
| | 6.2 Adverse Event Reporting | 14 |
| 7 | STUDY ADMINISTRATION | 15 |
| • | ~ | |

| 7.1 Treatment Assignment Methods | 12 |
|--|----|
| 7.2. Durin Connection and Management | 12 |
| 7.2 DATA COLLECTION AND MANAGEMENT | |
| 7.3 Confidentiality | |
| 7.4 REGULATORY AND ETHICAL CONSIDERATIONS | |
| 7.4.1 Data and Safety Monitoring Plan | 17 |
| 7.4.2 Risk Assessment | |
| 7.4.3 Potential Benefits of Trial Participation | |
| 7.4.4 Risk-Benefit Assessment | |
| 7.5 RECRUITMENT STRATEGY | 18 |
| 7.5.1 Consent | |
| 7.5.2 HIPAA Authorization | |
| 7.6 PAYMENT TO SUBJECTS/FAMILIES | |
| 7.6.1 Payments to parent for time and inconvenience (i.e. compensation) | 20 |
| 7.6.2 Payments to child for time, effort and inconvenience (i.e. compensation) | 20 |
| 7.6.3 Gifts | 20 |
| 8 PUBLICATION | 20 |
| 0 REFERENCES | 22 |

ABBREVIATIONS AND DEFINITIONS OF TERMS

ADHD Attention-Deficit/Hyperactivity Disorder AHRQ Agency for Healthcare Research and Quality

CHOP Children's Hospital of Philadelphia

CM Care Manager

EHR Electronic Health Records
GAS Goal Attainment Scaling
HP Healthy Pathway Scales
PCP Primary Care Provider

PCORI Patient-Centered Outcomes Research Institute

PeRC Pediatric Research Consortium Network
PFCC Patient and Family-Centered ADHD Care

PGI Preference and Goal Instrument
PRO Patient-Reported Outcomes

PROMIS Patient Reported Outcomes Measurement

Information System

REDCap Research Electronic Data Capture SACA Services Assessment for Children and

SDM Adolescents

Share-Decision Making

VPRS Vanderbilt Parent Rating Scales VTRS Vanderbilt Teacher Rating Scales

ABSTRACT

Context:

Health care for children with ADHD is fragmented between patients and families, teachers, and clinicians. This fragmentation can result in poorly coordinated services, and suboptimal outcomes for children with this common mental health disorder. Little attention has been devoted to developing and testing communication strategies as a means to improve ADHD care.

Objectives:

- 1. Determine the comparative effectiveness of an electronic patient portal (usual care, see Appendix 1), with the electronic patient portal combined with a care manager (CM, Appendix 2) to facilitate family-centered communication and treatment for children with ADHD.
- 2. Assess treatment initiation, adherence and family engagement as mediators of intervention treatment effects.
- 3. Geocode and conduct spatial analysis to explore individual, family and community factors that moderate intervention treatment effects.

Study Design:

This study is a prospective, randomized comparative effectiveness trial.

Setting/Participants:

This study will enroll 300 parent-child dyads in which the child has ADHD and is 5 through 12 years old from up to 15 outpatient pediatric primary care clinics in The Children's Hospital of Philadelphia (CHOP)'s Care Network. Eligible children must have an ADHD diagnosis and receive care at a participating clinic within the past 12 months. Children will be excluded if they and/or their parents/caregivers are non-English speaking, have a diagnosis of autistic spectrum disorder, conduct disorder, psychosis, bipolar disorder, or suicide attempt in the past 12 months. Participants will be randomized to either the patient portal only, or the patient portal combined with a Care Manger (CM) and will complete 3 follow-up visits over 9-12 months.

Study Interventions and Measures:

Families enrolled in the intervention will receive The ADHD portal and a CM. Participants will complete a screening to determine their treatment preferences and goals, and will be contacted weekly to every 3 months by the CM, who will provide education on common ADHD problems, assess treatment use, and identify new concerns. The CM will also communicate with their pediatric clinicians, mental health providers, and teachers to clarify family treatment preferences and goals, communicate information, coordinate care, and address emerging treatment issues.

Families enrolled in the usual care arm will receive care as usual from their PCP and access the ADHD portal to complete rating scales, view teacher rating scales, and download

educational handouts.

Primary study outcome measures are: Vanderbilt Parent and Teacher Rating Scales to measure ADHD Symptoms, ADHD Preference and Goal Instrument, Goal Attainment Scale, and Patient Reported Outcomes Measurement Information System short forms and Healthy Pathway Scales to measure patient-reported outcomes. Secondary outcome assessments will include measure patient and family engagement and treatment initiation and adherence. These measures will be completed at baseline, 3-5 months, 6-8 months, and 9-12 months following enrollment.

| PROTOCOL SYNOPSIS | | | | | | |
|--|---|--|--|--|--|--|
| Study Title Communication to Improve Shared-Decision Making in Att Deficit/Hyperactivity Disorder (ADHD) | | | | | | |
| Funder | Patient-Centered Outcomes Research Institute (PCORI) | | | | | |
| Clinical Phase | Phase III | | | | | |
| Study Rationale | Fragmentation in health care and poor communication across systems adversely impact engagement and adherence to treatment by children with ADHD and their families. Fragmentation of services for ADHD impairs communication and collaboration between families and primary care providers, mental health providers, and educators, and leads to suboptimal outcomes for children. | | | | | |
| | Fragmentation in the systems of care has been cited by a presidential commission as a major obstacle to effective care. To obtain treatment from diverse providers, families of affected children must negotiate the physical, mental health, and educational systems, but fragmentation in the system limits their ability to complete this task. Prior studies have documented that little communication and coordination exist among providers across different systems despite calls for better system integration. | | | | | |
| | Fragmentation in communication between providers has the potential to impair shared decision-making. To promote shared decision-making, we have developed an electronic health record (EHR)-linked portal to collect information from parents, teachers and clinicians on children's ADHD symptoms and treatment-related preferences and goals. We have also developed an ADHD care manager intervention manual. | | | | | |
| Study Objective(s) | Primary | | | | | |
| | • Determine the comparative effectiveness of an electronic patient portal designed to communicate family-centered preferences and goals for treatment of ADHD with providers and educators (tier 1) with the electronic patient portal combined with a Care Manger (CM)(tier 2) to facilitate communication for children with ADHD. | | | | | |
| | Secondary | | | | | |
| | Assess treatment initiation and adherence and family engagement as mediators of intervention treatment effects. Explore individual, family, and community factors that moderate intervention treatment effects Investigate test-retest reliability of PFCC survey | | | | | |

| Study Phases Screening Study Treatment | Screening: Families will be mailed recruitment letters signed by their PCP or practice, including a stamped self-addressed postcard to permit families to opt out. Families who do not opt out will be called to screen for eligibility and schedule a consent visit. |
|---|---|
| Study Duration | Each subject's participation will last 9-12 months. The entire study is expected to last 36 months |
| | Total Number of Sites: up to15 CHOP practices |
| Number Of Subjects | Total number of Subjects: 300 parent-child dyads Total Number at CHOP: 300 parent-child dyads |
| | Subjects with a diagnosis of any of the following in the past 12 months, as measured by self report: autistic spectrum disorder, conduct disorder, psychosis, bipolar disorder, suicide risk, or non-English speaking |
| | Exclusion Criteria |
| key criteria for Inclusion and Exclusion: | Ages 5 through 12 years old. Receiving ADHD treatment from participating practices. ADHD or ADD diagnosis code recorded in the past year. Parental/guardian permission and if appropriate, child assent. |
| Subject Population | collected at baseline, 3-5, 6-8, and 9-12 months. Inclusion Criteria |
| | Randomization will be stratified by practice, cliffd gender, and age groups (5 though 8 years old and 9 through 12 years old). Treatment assignment will be done at the time of enrollment following informed consent, and patient-reported outcomes |
| Study Design | Prospective, randomized comparative effectiveness trial. Participants will be randomized 1:1 to the ADHD portal (tier 1) or the ADHD portal plus CM (tier 2). Randomization will be stratified by practice, child gender, and |
| | The CM will follow up with families weekly to every 3 months. The CM will also communicate with the clinicians, mental health providers, and teachers. |
| Test Article(s) (If Applicable) | Patient portal with CM: The CM will meet with families at the beginning of the study to confirm their treatment preferences and goals. |
| | Evaluate intervention group outcome experience with care management and study feedback |
| - | Investigate intervention group parent satisfaction with the care manager |

[figure not shown]
Intervention: The CM will meet with families at the beginning of the study to confirm their treatment preferences and goals, and will contact families weekly to every 3 months to assess treatment use, identify new concerns, and assist families with problem-solving. The CM will also communicate with pediatric clinicians, mental health providers, and teachers to clarify family treatment preferences and goals and address emerging treatment issues. **Efficacy** ADHD Symptoms: Vanderbilt Parent and Teacher Rating Scales (VPRS and VTRS, Appendices 9 and 10) **Evaluations** Goal Attainment: ADHD Preference and Goal Instrument and Goal Attainment Scaling (Appendices 15 and 5) Patient-reported Outcome (PRO) Measures: Patient Reported Outcomes Measurement Information System (PROMIS) short forms and Healthy Pathway (HP) Scales (Appendix 17) Treatment initiation and adherence: Monthly EHR data review and the Services Assessment for Children and Adolescents (SACA) (Appendix 14) Family engagement: PFCC Questionnaire (Appendix 18) Satisfaction Survey: Investigate intervention group parent satisfaction with the care manager Subject safety will be monitored by adverse events, and **Safety Evaluations** follow-up surveys (Appendices 3 and 6). The research team will query participants at least every 6 months to determine if personal health information has been disclosed. **Statistical And Analytic** Study data will be collected and managed using the secure Plan web-based REDCap database at CHOP. ¹³⁸ Repeated measures longitudinal analysis that models baseline, 3-5 month, 6-8 month, and 9-12 month measurements as outcomes. For the primary outcomes of ADHD symptoms and goal attainment, and secondary PRO measures, both linear mixed effects and marginal (GEE) models will be implemented. DATA AND SAFETY The Principal Investigator is responsible for data quality MONITORING PLAN management and ongoing assessment of safety.

- Study data will be collected and managed using the secure web-based REDCap database at CHOP
- Data will be encrypted and transferred from its origin to the database housed in CHOP's secure data center.
- All data management and analysis will proceed on secure data and software servers that have daily back-up.
- All participants will be provided with a unique study identifier, which will permit linking of study measures in the REDCap database.

TABLE 1: SCHEDULE OF STUDY PROCEDURES

| Study Phase | Screening | Intervention | | | | | |
|--|---------------|--------------|------------|------------|-------------|---------------|--|
| Visit Number | Phone Call | 1 | 2 | 3 | 4 | 5 | |
| Study Days | | Baseline | 3-5 Months | 6-8 Months | 9-12 Months | 9.5-12 Months | |
| Review Inclusion/Exclusion Criteria | X`1 | | | | | | |
| Informed Consent/Assent | | X | | | | X | |
| Randomization | | X | | | | | |
| Demographics/Medical History | | X | | | | | |
| ADHD Symptoms | | X | X | X | X | | |
| Goal Attainment | | | X | X | X | | |
| Patient Reported Outcome Measures | | X | X | X | X | | |
| Treatment initiation and adherence | | X | X | X | X | | |
| PFCC Questionnaire | | | | | X | X | |
| Satisfaction Survey | | | | | X | | |
| Qualitative Interview | | | | | | X | |

FIGURE 1: STUDY DIAGRAM

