4 STUDY PROCEDURES

The study research materials will consist of parent- and child-reported instruments and will be separate from information entered into the ADHD portal. Parents will complete measures of treatment preferences and goals (ADHD PGI), ADHD symptoms (VPRS), and PRO at baseline. They will complete a measure of engagement at 0 and 9-12 months. They will also complete VPRS, and goal attainment (GAS) at 3-5 months, 6-8 months, and 9-12 months. Parents will complete a measure of treatment initiation and adherence (SACA) at 9-12 months. Parents and children, as appropriate, will complete the PRO measures (school performance, student engagement, peer relationships, family belonging, and teacher connectedness) at 9-12 months. Parents will complete PFCC measure at 9-12 months and up to 40 participants will complete second PFCC measure. Parents and children will complete the study measures using a subject-specific embedded email link to a REDCap survey on a secure server. Tier 1 will consist of an electronic patient portal designed specifically for ADHD (Appendix 1). Tier 2 will consist of the electronic patient portal combined with an ADHD CM (Appendix 2). Tier 2 also will permit us to test whether the addition of a CM can improve outcomes for specific patient subgroups including patients from urban communities, of minority, or lower socioeconomic status that might be less engaged with the portal (Specific Aim #3). Tier 2 will also be asked to complete a satisfaction survey about using the care manager (Appendix 19). In addition, 40 Tier 2 participants will be asked to do an interview about their experience with care management and for study feedback (Appendix 20).

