4.5 Efficacy Evaluations

4.5.1 Diagnostic Tests, Scales, Measures, etc.

Methods and timing the measures that will be used to assess efficacy

| Study Measures and Timing | | | | | |
|---------------------------|------------------|----------------------------------|-------------------|--|--|
| Measure | Source | Time to Complete (minutes) | Timing (months) | | |
| ADHD PGI (primary) | Parent | 5 | 0 | | |
| VPRS (primary) | Parent | 5 | 0, 3-5, 6-8, 9-12 | | |
| VTRS (primary) | Epic records | n/a (usual care) | n/a (usual care) | | |
| GAS (primary) | Parent | 1-2 | 3-5, 6-8, 9-12 | | |
| Engagement (M) | Parent | 3-5 | 3 | | |
| Medications (M) | her | 0 | 1-9-12 | | |
| SACA (M) | Parent | 10 | 9-12 | | |
| PROs (secondary) | | | | | |
| School performance | Child, Parent | 3-5 | 0,9-12 | | |
| Student engagement | Child, Parent | 3-5 | 0,9-12 | | |
| Peer relationships | Child, Parent | 3-5 | 0,9-12 | | |
| Family belonging | Child, Parent | 3-5 | 0,9-12 | | |
| Teacher connectedness | Child, Parent | 3-5 | 0,9-12 | | |
| PFCC Questionnaire | Parent | 10 | 9-12, 9.5-12 | | |
| Satisfaction Survey | Parent | 10 | 9+ | | |

| Qualitative Interview | Parent | 30 | 9+ | | |
|---|--------|----|----|--|--|
| School performance, student engagement, and teacher connectedness are | | | | | |
| Healthy Pathways scales; peer relationships and family belonging are PROMIS scales (M) denotes a mediator | | | | | |

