In order to assess family engagement, a series of items were created from review of the literature and prior instruments in other fields. We utilized confirmatory factor analyses to find distinct domains for which each item loading was greater than 0.7. Our first round of analyses resulted in 3 factors: patient/family centered care, communication, and understanding. Upon presentation to the study team, there were several items that were dropped from the initial domains, but additional items resonated with the team as important concepts in which the intervention was focused. Thus, the study team came to consensus on items that should be included. These items represented four conceptual domains. The 4factor structure was supported in confirmatory factor analyses. While the patient/family centered care and understanding domains remained the same, the original communication domain was split into two factors, resulting in the following domains: care team accessibility; patient and family-centered care; communication among members of the care team, and understanding of ADHD. To compare patients in the tier 1 and tier 2 groups by engagement status, we utilized t-tests for each of the four domains separately. Further, linear mixed effects models were implemented for each engagement domain as the outcome, with intervention status and season as covariates clustering for clinic site. We further assessed for item responsiveness using item response methods.

We explored treatment initiation and adherence via the services assessment for children and adolescents (SACA) and medication status.⁹⁵ On the SACA, patients reported service use ever, as well as service use within the past 9 months. Categorizations include any service use, ambulatory service use (any community mental health or outpatient clinic, private professional, or in-home provider), and overnight stay (psychiatric or medical unit, residential treatment center, group home, or foster home). Differences between intervention groups and treatment initiation were assessed via Chi-square tests. In addition, treatment initiation and adherence were assessed via medication status throughout the study period. At baseline and 3, 6, and 9 month follow up surveys, participants were asked as to whether their child was on or off medication. If data was missing for a particular timepoint, we utilized medication status within the EHR if available.

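### The SACA is given once, at 9-12 months, so the SAP's Aim 2 comparison of service use cannot be read as treatment initiation or adherence

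*Protocol*

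**What the plan says.** **Schedule.** The row in Protocol Table 1 reads "Treatment initiation and adherence | | X | X | X | X", that is, baseline and three follow-ups. The Abstract, after listing the primary and secondary measures, adds: "These measures will be completed at baseline, 3-5 months, 6-8 months, and 9-12 months following enrollment". The Synopsis (Efficacy Evaluations) gives the content of the domain: "Monthly EHR data review and the Services Assessment for Children and Adolescents (SACA".

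**Timing of the SACA.** Section 4 says: "Parents will complete a measure of treatment initiation and adherence (SACA) at 9-12 months". The measures table in 4.5.1 agrees: "SACA (M) | Parent | 10 | 9-12". The other component of the domain appears there as "Medications (M) | her | 0 | 1-9-12", where the source is evidently a misprint for EHR.

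**Definitions.** Section 5.5 (Aim 2) defines initiation as beginning a treatment plan that the family prefers at least moderately, and adherence as remaining in treatment through month 9-12. It names the ADHD PGI as the instrument, but 4.5.1 gives the PGI at month 0 only.

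**Analysis.** Under SAP Aim #2, on the SACA "patients reported service use ever, as well as service use within the past 9 months". Answers are grouped as any, ambulatory or overnight use, and then: "Differences between intervention groups and treatment initiation were assessed via Chi-square tests". Medication status is handled separately. It is asked at baseline and at 3, 6 and 9 months, with the EHR filling gaps.

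**The concern.** Initiation is a change from not using a service to using it. A single recall at the end of follow-up, with no starting state, records whether a service was used, not whether it was begun. The SAP has no new-start category and makes no adjustment for earlier use. Adherence has the same difficulty: one early visit in the recall window counts the same as a service kept up to the end.

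The SAP dropped the formal mediation tests and made between-arm differences in engagement, initiation and adherence the Aim 2 result. A null chi-square could therefore be read as the care manager not helping families to start services. A positive one could be read as more starts when it reflects better retention of families already in services. The data as scheduled cannot tell these apart.

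**Working it through.** **1. Can any other item supply the missing starting state?**

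- *The ever item.* No for ever with yes for the past 9 months is impossible. Yes for both fits a new starter and a continuing user alike. Ever also counts use before randomisation, which the intervention cannot change.
- *The Table 1 baseline mark.* The domain is a composite. The SAP's baseline medication question can meet the mark for medication; nothing meets it for services.
- *The ADHD PGI.* It is given once, at month 0, and records preferences and goals.
- *Outpatient visits from the EHR.* Section 4.4.1 lists them for abstraction, but neither document uses them to measure the start of non-drug services.

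**2. Reproduce the plan's figure.** Inputs from 5.5: 120 per arm, 50% vs 70%. Two-sided alpha 0.05 is assumed, since the documents state none. With p̄ = (p1 + p2)/2,

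power = Φ{ [ |p2 − p1|·√n − 1.96·√(2p̄(1 − p̄)) ] / √(p1(1 − p1) + p2(1 − p2)) }

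= Φ{ [0.20 × 10.954 − 1.96 × √0.48] / √0.46 } = Φ(1.228) = 0.890, matching the stated 0.89. With 75% the result is 0.983, matching the stated figure of more than 0.98.

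**3. What the single SACA would show.** Let q be the share of each arm already using services (assumed; not in the documents) and c1, c2 the proportions of those users who continue in tier 1 and tier 2. Apply 50% vs 70% to the non-users. Then

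- observed use in tier 1 = q·c1 + (1 − q)·0.50
- observed use in tier 2 = q·c2 + (1 − q)·0.70
- observed difference = 0.20·(1 − q) + q·(c2 − c1)

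The first term is initiation, diluted by (1 − q). The second is continuation.

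**4. All existing users continue (c1 = c2 = 1).** The last two columns show the comparison restricted to baseline non-users, 50% vs 70%, with n = 120(1 − q) per arm.

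| q | Observed use | Difference | Power, n = 120 | Non-users per arm | Power, non-users |
|---|---|---|---|---|---|
| 0 | 50% vs 70% | 20 points | 0.89 | 120 | 0.89 |
| 0.1 | 55% vs 73% | 18 points | 0.83 | 108 | 0.86 |
| 0.3 | 65% vs 79% | 14 points | 0.68 | 84 | 0.76 |
| 0.5 | 75% vs 85% | 10 points | 0.49 | 60 | 0.61 |

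Restriction keeps the 20-point estimate at every q and recovers part of the power, but not 0.89.

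**5. Vary continuation at q = 0.3.**

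- Equal at 70%: 56% vs 70%, 14 points, power 0.61. The dilution is the same whenever c1 = c2.
- 70% vs 90%: 0.21 + 0.35 = 56% against 0.27 + 0.49 = 76%, 20 points. There is no visible dilution, but 6 of the 20 points are continuation (0.3 × 0.20).
- 70% vs 95%: 56% vs 77.5%, 21.5 points, larger than the initiation effect.

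The size and direction of the distortion therefore depend on c2 − c1, which a single SACA cannot estimate.

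**The case against.** Several arguments on the other side are sound.

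- *Table 1 does not name the SACA.* A reader might infer that the plan schedules a baseline SACA and then omits it. The documents do not support that. The row is a domain, and medication status can meet its baseline mark. The Abstract sentence is a loose summary: it also covers goal attainment, which Table 1 does not place at baseline.
- *The comparison is randomised.* Prior use is balanced in expectation. Use in the past 9 months, asked at 9-12 months, falls essentially after randomisation. It is a valid contrast of service use between arms; only its reading as initiation or adherence fails.
- *Dilution is not certain.* A reader might infer that the design must shrink any arm difference. Step 5 shows otherwise, and Protocol 4.2 gives the care manager the task of promoting adherence, so unequal continuation is plausible.
- *Prior use may be modest.* A reader might infer that recorded use was mostly fixed before randomisation, since inclusion criterion 2 requires current ADHD treatment. But that treatment comes from primary care practices, whereas the SACA ambulatory category covers mental health and in-home providers. Section 1.3 says, as background, that fewer than half of treated children receive behavioral treatment. In the model above, at q = 0.2, prior users make up only 0.20/0.60 = 33% of tier 1 use and 0.20/0.76 = 26% of tier 2 use.
- *The power rates are borrowed.* Section 5.5 applies 50% vs 70% to all 120 children per arm, for starting a preferred plan, not to non-users of SACA services.
- *The SAP may not have tested ever use.* The chi-square sentence does not say which recall window was used. Medication status is followed over time, so the SAP is not without a repeated measure of adherence for drugs.
- *Consequence.* Aim 2 is secondary, and the SAP describes this work as exploratory.

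These points limit the claim about size and direction. They do not supply a starting state for services, so the mislabelling stands.

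**Conclusion.** The point holds as a mismatch between what Aim 2 claims to measure and what a single SACA can show. Following the SAP as written yields a comparison of service use, which is neither initiation nor adherence as Protocol 5.5 defines them. It is not confounding. With equal continuation in both arms, an initiation difference is reduced by the factor (1 − q). With unequal continuation, initiation and continuation are mixed and the direction is unknown.

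The figures of 18, 14 and 10 points (power 0.83, 0.68 and 0.49) are an illustration. They rest on assumed q of 0.1, 0.3 and 0.5, full continuation in both arms, the protocol's 50% vs 70% moved to non-users, 120 per arm and two-sided 0.05. The documents do not give q, so they do not show that a real effect was or will be missed.

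**What to change.** **If the SACA can still be given at baseline:** add it at visit 1, at about 10 minutes of parent time by the protocol's own estimate. In SAP Aim #2, define service initiation as use at follow-up of a category not in use at baseline, and compare arms among baseline non-users. Alternatively, model use in the past 9 months with baseline use as a covariate. That estimates an effect on use given prior use, and should be described so. Restate power for the non-user comparison, because 0.89 will not apply.

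**Where no baseline SACA exists:** the SAP is dated 6/28/19 and written in the past tense, so this probably applies. Report the SACA result as service use in the past 9 months, not as initiation or adherence. Do not interpret ever use as an intervention effect, and state which recall window each chi-square test used. This costs only relabelling.

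**In either case:** reconcile Table 1, section 4, the 4.5.1 measures table and section 5.5 on which instrument measures initiation and adherence, for drugs and for services separately, and when. Section 5.5 in particular names the PGI, which is given only at month 0.
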